3.0 Patient Eligibility

3.1 Eligibility Criteria

NOTE: Phase I Only – Prior to discussing protocol entry with the patients **AND** prior to registering in the electronic data capture (eDC) system, call the PrECOG Project Manager to ensure that a place on the protocol is open to the patient. The Project Manager contact information is located in the Study Reference Manual.

3.11 ≥ 18 years of age.

3.12 Diagnosed with previously treated multiple myeloma (please see Appendix II for definition of myeloma).

3.13 Patients must have measurable disease assessed by one of the following ≤ 21 days prior to registration:

- Serum monoclonal protein ≥ 1 g by protein electrophoresis*
- >200 mg of monoclonal protein in the urine on 24 hour electrophoresis*
- Serum immunoglobulin free light chain ≥ 10 mg/dL **AND** abnormal serum immunoglobulin kappa to lambda free light chain ratio
- Monoclonal bone marrow plasmacytosis $\geq 30\%$ (evaluable disease)

*NOTE: If both serum and urine m-components are present, both must be followed in order to evaluate response.

3.14 All previous cancer therapy including chemotherapy, radiation, hormonal therapy and surgery, must have been discontinued ≥ 2 weeks prior to registration.

3.15 ECOG Performance Status (PS) 0, 1, or 2 (see Appendix III).

3.16 Acceptable organ and marrow function ≤ 21 days prior to registration as defined below:

- Absolute neutrophil count ≥ 1000 cells/mm³
- Platelet count $\geq 75,000$ cells/mm³
- Total bilirubin ≤ 2 mg/dL.
- AST (SGOT) and ALT (SGPT) $\leq 3 \times$ ULN

3.17 Renal impairment at baseline as measured by serum creatinine clearance (CrCl) ≤ 60 mL/min ≤ 21 days prior to registration (see Appendix IV).

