4.0 Test Schedule

*Treatment should begin \leq 7 working days from registration
 *Variations of +/- 3 days of the scheduled visits are permitted

	\leq21 days prior to registration	Cycle 1 only	For Each of the First Four Cycles				End of Cycle 4	Day 1 Each additional cycle ¹⁷	Day 1 of cycle 9 or at end of treatment	Follow-Up ^{16,18}
			Day 6	Day 1	Day 8	Day 15				
History & Exam, Wt., PS Assessment	X		X ¹²				X	X	X	
Height	X									
CBC w/differential	X		X ¹³	X	X	X		X ¹³		
Chemistry Panel (Na,K,Ca,AST,ALT,Alk Phos,Total Bili, Glucose, Creatinine, Albumin)	X		X	X ¹⁴	X ¹⁴	X ¹⁴	X	X	X	
Serum Creatinine Clearance ¹	X		X				X	X	X	
LDH, Beta-2 Microglobulin, C-Reactive Protein	X						X		X	
Serum TSH ²	X		X					X		
SPEP ³	X		X ¹²				X	X	X	
UPEP (24hr collection) ³	X		X ¹²				X	X	X	
Quantitative Immunoglobulins ³	X		X ¹²				X	X	X	
Serum Free Light Chains ³	X		X ¹²				X	X	X	
Immunofixation-Serum & Urine ⁴	X						X		X	
Bone Marrow Biopsy w/aspirate	X ⁵						X ¹⁵		X ¹⁵	X ¹⁹
Bone Marrow-FISH, cytogenetics	X ⁵									
Metastatic Bone Survey w/ long bones	X ⁵						X		X	
Chest X-Ray	X									

	≤21 days prior to registration	Cycle 1 only	For Each of the First Four Cycles					End of Cycle 4	Day 1 Each additional cycle¹⁷	Day 1 of cycle 9 or at end of treatment	Follow-Up^{16,18}
			Day 6	Day 1	Day 8	Day 15	Day 22				
ECG	X										
Pharmacokinetics ^{6, R}		X ⁶									
INR ⁷			X ⁷	X ⁷	X ⁷	X ⁷	X ⁷	X ⁷	X ⁷	X ⁷	
Pregnancy Testing ⁸	X ⁸		X ⁸						X ⁸	X ⁸	
Education and Counseling Guidance Document ⁹			X ⁹						X ⁹	X ⁹	
Dispense Study Drug ¹⁰			X ¹⁰						X ¹⁰		
Study Drug Compliance (Medication Diary)			X						X	X	
Adverse Event Assessment ¹¹				X	X	X	X ¹⁶	X	X ¹⁶	X ¹⁶	
Survival and Malignancy Surveillance											X ¹⁸

1. Creatinine clearance will be estimated using the Cockcroft-Gault formula. If the patient is >65 y/o and creatinine is <1, use 1 as serum creatinine value to calculate the creatinine clearance, see Appendix IV.
2. To be completed at baseline and then every 3 months.
3. Required at baseline, and then only required if used to assess disease response (see Section 11.2, Table 11.2).
4. Is required at study entry only if not previously performed or test results not available. If complete response is seen a 2nd immunofixation should be performed 4 weeks later to confirm. Urine immunofixation is only required if positive at study entry.

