11.2 Clarification of Test Indications

Listed below are the minimal required tests required to assess response based on the characteristics of their disease at on study. Response is to be assessed at the end of each treatment cycle within 3 days prior to the start of the next cycle.

Table 11.2 Tests Required To Assess Response (Must Be Done At Each Disease Measurement Visit)				
On Study Baseline Value	SPEP	24 hr UPEP	Ig FLC	BM Bx
Serum M-spike ≥ 1 g/dl, and urine M-spike ≥ 200 mg/24 hrs	X	X		
Serum M-spike ≥ 1 g/dl, but urine M-spike < 200 mg/24 hrs	X			
Serum M-spike < 1 g/dl, and urine M-spike ≥ 200 mg/24 hrs		X		
Serum M-spike < 1 g/dl, urine M-spike < 200 mg/24 hrs, but involved Ig FLC is ≥ 10 mg/dL			X	
Serum M-spike < 1 g/dl, urine M-spike < 200 mg/24 hrs, involved Ig FLC is < 10 mg/dL, bone marrow $\geq 30\%$ plasma cells				X ^a
Immunofixation studies of both serum and urine are required to document CR regardless of registration values, and in addition FLC measurement and bone marrow immunophenotyping is required to document sCR.				

^a*Exception: bone marrow biopsy does not have to be confirmed.*

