11.5 Response and Progression

Criteria for response and progression are listed in Table 11.5.

Table 11.5

CATEGORY	RESPONSE CRITERIA ^a
stringent Complete Response (sCR)	
 • CR as defined below plus all of the following 
 ○ Normal serum FLC ratio ○ Absence of clonal cells in bone marrow by immunohistochemistry or immunofluorescence ^b
Complete Response (CR)	
 • Negative immunofixation of the serum and urine • If at on study, the only measurable non-bone marrow parameter was FLC, normalization of FLC ratio • <5% plasma cells in bone marrow • Disappearance of any soft tissue plasmacytomas
Very Good Partial Response (VGPR)^c	
 • PR as defined below plus all of the following: 
 ○ Serum and urine M-component detectable by immunofixation but not on electrophoresis or ○ If at on study, serum measurable, $\geq 90\%$ or greater reduction in serum M-component ○ Urine M-component <100 mg per 24h
Partial Response (PR)	
 • One of the following: 
 ▪ If at on study, serum and urine measurable, a $\geq 50\%$ reduction of serum M-protein and reduction in 24h urinary M-protein by $\geq 90\%$ or to <200 mg per 24h ▪ If at on study, only serum measurable (but urine not), a $\geq 50\%$ reduction of serum M-protein ▪ If at on study, urine measurable (but serum not), a reduction in 24 h urinary M-protein by $\geq 90\%$ or to <200 mg per 24h ▪ If at on study, the only measurable non-bone marrow parameter was FLC, a $\geq 50\%$ decrease in the difference between involved and uninvolved FLC levels or a 50% decrease in level of involved FLC with 50% decrease in ratio ▪ If at on study, the bone marrow was only measurable parameter, $\geq 50\%$ reduction in bone marrow plasma cells is required in place of M-protein, provided baseline percentage was $\geq 30\%$ • In addition to the above criteria, if a plasmacytoma present at baseline, $\geq 50\%$ reduction in the size of soft tissue plasmacytomas is also required

Stable Disease (SD)	Not meeting criteria for CR, VGPR, PR or progressive disease

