Progressive Disease (PD)	
Any one or more of the following:
 
 • Increase of 25% from lowest confirmed response in: 
 ▪ Serum M-component (absolute increase must be ≥ 0.5 g/dl)^c ▪ Urine M-component (absolute increase must be ≥ 200 mg/24h) ▪ If at on study, only the only measurable non-bone marrow parameter was FLC, the difference between involved and unininvolved FLC levels (absolute increase must be >10 mg/dl) ▪ Bone marrow plasma cell percentage (absolute % must be 10%)^d • Definite development of new bone lesions or soft tissue plasmacytomas or definite increase in the size of existing bone lesions or soft tissue plasmacytomas • Development of hypercalcemia (corrected serum calcium >11.5 mg/dl) that can be attributed solely to the plasma cell proliferative disorder
Relapse from CR or sCR	
Patient who has achieved confirmed CR who has any one or more of the following:
 
 • Reappearance of serum or urine M-protein by immunofixation or electrophoresis • Development of $\geq 5\%$ plasma cells in the bone marrow^d • Appearance of any other sign of progression (e.g., new plasmacytoma, lytic bone lesion, or hypercalcemia)

^a All response categories require two consecutive assessments made at any time before the institution of any new therapy; complete and PR and SD categories also require no known evidence of progressive or new bone lesions if radiographic studies were performed. Radiographic studies are not required to satisfy these response requirements. Bone marrow assessments need not be confirmed. Each category, except for stable disease, will have a working subcategory of “unconfirmed” [prefix ‘u’] to designate first time point at which response category MAY have been achieved if confirmed.

^b Presence/absence of clonal cells is based upon the k/λ ratio. An abnormal k/λ ratio by immunohistochemistry and/or immunofluorescence require a minimum of 100 plasma cells for analysis. An abnormal ratio reflecting presence of an abnormal clone is k/λ of $>4:1$ or $<1:2$.

^c For progressive disease, serum M-component increases of ≥ 1 gm/dl are sufficient to define relapse if starting M-component is ≥ 5 g/dl. Positive immunofixation alone in a patient previously classified as CR will not be considered progression.

^d Relapse from CR has the 5% cutoff versus 10% for other categories of relapse.

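### The minimum tests required by footnote 3 and Table 11.2 cannot establish PD or VGPR as Table 11.5 defines them, and footnote 4 contradicts Table 11.2 on CR

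*Protocol*

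**What the plan says.** - **Protocol 4.0, footnote 3** (attached to SPEP, UPEP, quantitative immunoglobulins and serum free light chains): "Required at baseline, and then only required if used to assess disease response", with a reference to Table 11.2.
- **Protocol 11.2, Table 11.2**, titled "Tests Required To Assess Response (Must Be Done At Each Disease Measurement Visit"): if serum is at least 1 g/dl "but urine M-spike < 200 mg/24 hrs", only SPEP is marked. In the mirror case (serum below 1 g/dl, urine at least 200 mg/24 h) only UPEP is marked. The text above the table calls these minimal tests.
- **Protocol 11.5, Table 11.5, PD row**: any one criterion suffices. Two of them are a 25% rise from the lowest confirmed value in the serum M-component (at least 0.5 g/dl) or in the urine M-component ("Urine M-component (absolute increase must be" at least 200 mg/24 h). Neither line requires measurability at entry; the FLC line next to them does.
- **Table 11.5, VGPR row**: PR plus either "Serum and urine M-component detectable by immunofixation but not on electrophoresis", or at least a 90% serum reduction with urine below 100 mg per 24 h.
- **Protocol 3.13, note**: "If both serum and urine m-components are present, both must be followed in order to evaluate response".
- **Protocol 4.0, footnote 4**: "Urine immunofixation is only required if positive at study entry". **Table 11.2, last row**: immunofixation studies of both serum and urine "are required to document CR regardless of registration values".
- **SAP 5.1** adopts Tables 11.2 and 11.5 together and does not reconcile them.

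**The concern.** The test schedule and the endpoint definitions use different sets of components. A patient with one measurable and one smaller, detectable component is tested on the first only, yet can meet PD on the second. If the second rises while the first falls or holds, PD as defined can go unseen, or be dated only when another criterion is met. PFS and duration of response both end at documented progression, so they would be lengthened.

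VGPR has a similar gap: a site doing only the required tests in a serum-only patient has no urine value with which to support the call. For CR, footnote 4 and Table 11.2 give opposite instructions for a patient whose urine immunofixation was negative at entry, so CR may be documented differently from site to site.

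**Working it through.** **1. Required tests against definitions, by baseline pattern**

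| Baseline | Table 11.2 requires | PD can be met on | VGPR needs |
|---|---|---|---|
| Serum ≥1 g/dl, urine <200 mg/24 h | SPEP | serum or urine | serum and urine |
| Serum <1 g/dl, urine ≥200 mg/24 h | UPEP | serum or urine | urine; serum too by the electrophoresis route |
| Both measurable | SPEP and UPEP | serum or urine | serum and urine |

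Only the last row is consistent throughout. In the first row VGPR needs a urine result by either route. PD is also judged against the lowest confirmed value; for a component not followed, the only required value is the baseline one.

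**2. Two illustrative patients, using the protocol's thresholds** (each later value assumed to hold on two consecutive assessments)

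- Serum 2.0 to 0.9 g/dl: (2.0 − 0.9)/2.0 = 55% fall, which meets the PR row. Urine 180 to 600 mg/24 h: +420 mg, 420/180 = +233%, which meets the urine PD line. No UPEP is required.
- Urine 1000 to 80 mg/24 h: 920/1000 = 92% fall, which meets the PR row. Serum 0.8 to 1.4 g/dl: +0.6 g/dl, 0.6/0.8 = +75%, which meets the serum PD line. No SPEP is required.

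**3. Which endpoint is affected**

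- Rise after PR is confirmed: the PR stands. PD is late or missed, so PFS and duration of response are too long.
- Confirmed rise before PR is confirmed: the patient meets both the PR and the PD row, and Table 11.5 does not say which prevails. Only here can the PR-or-better count change.
- VGPR and CR: both already count as success, so these gaps affect depth of response only.

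**4. Sensitivity of the decision rule**

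The plan's figures first. P(X ≥ 31) for X ~ Binomial(63, p) at p = 0.40, 0.45, 0.50, 0.55, 0.60 is 0.0873, 0.2922, 0.5993, 0.8533, 0.9687. Protocol 16.35 states 0.09, 0.29, 0.60, 0.85, 0.97, so all five reproduce.

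One patient is 1/63 = 1.6 percentage points. The documents do not give the share with a detectable but non-measurable second component, nor how often it diverges. Assume 20–40% (13 to 25 of 63) and 5–10% of those:

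- 13 × 0.05 = 0.65 patients (1.0% of 63); 25 × 0.10 = 2.5 patients (4.0%).
- At a true rate of 0.40, adding 1% gives P(X ≥ 31) = 0.116; adding 4% gives 0.240.

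This is an upper range, because it treats every diverging patient as a false PR. If divergence is independent of response in the followed component, multiply by the response rate: 0.65 × 0.40 = 0.26 to 2.5 × 0.55 = 1.4 patients. At the null rate the ceiling is 2.5 × 0.40 = 1.0 patient (1.6%), which puts the probability between 0.116 (1%) and 0.151 (2%). The timing condition in step 3 lowers it further.

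**The case against.** Much of the case on the other side stands.

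- **Table 11.2 is a floor.** A reader might infer that testing of the smaller component is stopped, or that every VGPR in a serum-only patient lacks its urine value. The documents do not support that: extra tests are allowed, and the value may exist. What remains is that it is not required, so detection varies by site.
- **The 3.13 note is ambiguous.** Its asterisk hangs on the two criteria that set measurable levels, so a component that is present may mean one that is measurable. That reading agrees with Table 11.2. The note supports the point but does not prove it; the conflict with the PD and VGPR rows does not depend on it.
- **The PR row agrees with Table 11.2.** It judges PR on the measurable component, and the first illustrative patient does meet it. A reader might infer that the plan counts progressing patients as responders in general. That needs a confirmed rise before PR is confirmed, and a precedence rule that Table 11.5 does not contain.
- **PD needs two consecutive assessments.** A single raised value is at most unconfirmed PD.
- **Other criteria can detect progression.** Bone lesions, plasmacytomas and hypercalcemia count as PD. Calcium is measured on day 1 of each cycle, and a bone survey is scheduled at the end of cycle 4 and at cycle 9 or end of treatment. Immunofixation is scheduled at the same two times but is qualitative. None of these shows the quantitative rise in the PD row.

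The footnote 4 contradiction is not answered by any of this.

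**Conclusion.** The point holds as an inconsistency between the test schedule and the endpoint definitions. The minimum tests cannot establish PD on a component below the measurable level, or VGPR in serum-only patients, as Table 11.5 defines them. The likely consequences are upward bias in PFS and duration of response, and VGPR calls whose support varies by site. Footnote 4 and Table 11.2 cannot both be followed for CR when urine immunofixation was negative at entry.

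It would go too far to say that the primary result is inflated by a known amount. The 0.65 to 2.5 patients are an upper range resting on two assumed shares; the documents give no frequency, and the true effect on the PR-or-better count may be nil. Neither the VGPR gap nor the CR gap can change that count.

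**What to change.** 1. Delete the last sentence of footnote 4, so that CR follows the last row of Table 11.2.
2. Add to Table 11.2 that SPEP and 24-hour UPEP are both done when VGPR or better is first recorded, in patients to whom the VGPR category applies (it is not available to those followed by FLC or marrow only).
3. Reconcile footnote 3 and Table 11.2 with the PD row: require both SPEP and UPEP at each disease assessment in patients with both components detectable on baseline electrophoresis. State in Table 11.5 that confirmed PD on either component takes precedence over PR.

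The tests are already rows in the schedule. The cost is an amendment to two footnotes and two tables, extra 24-hour urine collections in a subset, and possibly slightly fewer VGPR and PR calls. The precedence statement touches the definition of the primary endpoint, so it should be listed as such a change and carried into the SAP. A component not detectable at baseline would still go untested until VGPR or better is recorded; the amendment should say that this is accepted.

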2.2 Secondary Objectives

2.21 To describe the overall survival, progression-free survival, duration of response, and time to treatment failure of myeloma patients with impaired renal function treated with lenalidomide and dexamethasone.

2.22 To evaluate the safety profile of lenalidomide given in combination with weekly dexamethasone in myeloma patients with impaired renal function.

2.23 To describe renal function over time and to evaluate the safety profile of a onetime increase in lenalidomide dose at least 2 cycles after start of treatment due to improved renal function.

2.24 To determine the pharmacokinetics of lenalidomide administration in myeloma patients with impaired renal function (pharmacokinetic analysis will be performed in up to 12 consented Mayo Clinic subjects treated during the Phase II component of the trial only).

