5. Bone marrow (with aspirate/FISH/cytogenetics) and skeletal survey may be used if performed ≤90 days of study enrollment.
6. Only applies to selected Mayo Clinic subjects registered to the Phase II component. Pharmacokinetics of lenalidomide: 5cc of blood is to be drawn and put into an EDTA tube at the following time points on Day 6 of Cycle 1: 0 (pre-dose), 0.5, 1, 1.5, 2, 3, 4, 6, 8, 24 hr at all dose groups and at 48 and 72 hr for patients in Group B with severe renal impairment or in Group C on dialysis (hemodialysis or peritoneal dialysis). Please see Section 14.2 for processing procedures. Pharmacokinetic samples will be collected from up to 12 Mayo Clinic participants with a minimum of two patients in each group (Groups A, B and C) of the Phase II component.
7. Treatment with Coumadin should be used with caution. If a patient is being treated with Coumadin, close monitoring of INR is required.
8. Pregnancy tests for females of childbearing potential. A female of childbearing potential (FCBP) is a sexually mature female who: 1) has not undergone a hysterectomy or bilateral oophorectomy; or 2) has not been naturally postmenopausal (amenorrhea following cancer

therapy does not rule out childbearing potential) for at least 24 consecutive months (e.g., has had menses at any time in the preceding 24 consecutive months). Pregnancy tests must occur within 10–14 days prior to initiation of Cycle 1 of lenalidomide and again within 24 hours prior to initiation of Cycle 1 of lenalidomide. FCBP with regular or no menstruation must have a pregnancy test weekly for the first 28 days and then every 28 days while on lenalidomide therapy (including breaks in therapy); at discontinuation of lenalidomide and at Day 28 post the last dose of lenalidomide. Females with irregular menstruation must have a pregnancy test weekly for the first 28 days and then every 14 days while on lenalidomide therapy (including breaks in therapy), at discontinuation of lenalidomide and at Day 14 and Day 28 post the last dose of lenalidomide (see Appendix V: Risks of Fetal Exposure, Pregnancy Testing Guidelines and Acceptable Birth Control Methods).

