$$\text{CrCl (mL/min)} = \frac{(140 - \text{age}) \times (\text{weight, kg})}{72 \times (\text{serum creatinine, mg/dL})}$$

Females:

$$\text{CrCl (mL/min)} = \frac{(140 - \text{age}) \times (\text{weight, kg})}{72 \times (\text{serum creatinine, mg/dL})} \times 0.85$$

If the patient is >65 y/o and creatinine is <1, use 1 as serum creatinine value to calculate the creatinine clearance.

7.12 Phase II Component:

- Lenalidomide at assigned dose (as determined by studies in Phase 1 component)
- Dexamethasone 40 mg orally on days 1, 8, 15 and 22
- Anticoagulation (see Section 9.4)

The dose for lenalidomide will be determined for each group in the Phase 1 portion of the study. Each cycle is 28 days. All groups get a 7 day rest (days 22-28) from lenalidomide. Dosing will be in the morning at approximately the same time each day. Only one cycle of study drug will be supplied to the patient each cycle. Lenalidomide capsules should be swallowed whole, and should not be broken, chewed or opened. If a dose of lenalidomide is missed, it should be taken as soon as possible on the same day. If it is missed for the entire day, it should not be made up (this applies to all dosing schedules). For patients in Group C, when a lenalidomide treatment day occurs on a dialysis day, lenalidomide must be taken after dialysis. Patients who take more than the prescribed dose of lenalidomide should be instructed to seek emergency medical care if needed and contact study staff immediately.

Dexamethasone will be given at a fixed dose of 40 mg by mouth once weekly on a 28 day treatment cycle. If a dose of dexamethasone is missed, it is up to the treating physician whether the dose should be made up. In addition, continuing dexamethasone if lenalidomide is stopped is also at the discretion of the treating physician.

Treatment is to be continued as tolerated until disease progression, intolerable toxicity or patient refusal.

7.2 Phase I Dose Escalation and Determination of MTD.

7.21 Dose Escalation of Lenalidomide:

Table 7.211: Group A = Patients with a 30-60 CrCl (mL/min)[□]

Dose Level		Dose	Treatment Day	Rest Day	Route
1*	Lenalidomide	10 mg	1-21	22-28	Orally
2	Lenalidomide	15 mg	1-21	22-28	Orally
3	Lenalidomide	25 mg	1-21	22-28	Orally

Table 7.212: Group B = Patients with CrCl <30 mL/min who are NOT on dialysis[△]

Dose Level		Dose	Treatment Day	Rest Day	Route
1*	Lenalidomide	15 mg	Every other day, days 1-21	22-28	Orally

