2	Lenalidomide	25 mg	Every other day, days 1-21	22-28	Orally
3	Lenalidomide	15 mg	1-21	22-28	Orally
4	Lenalidomide	25 mg	1-21	22-28	Orally

Table 7.213: Group C = Patients with CrCl <30 mL/min who are on dialysis^{#◊}

Dose Level		Dose	Treatment Day	Rest Day	Route
1*†	Lenalidomide	5 mg	1-21 [£]	22-28	Orally
2	Lenalidomide	10 mg	1-21 [£]	22-28	Orally
3	Lenalidomide	15 mg	1-21 [£]	22-28	Orally
4	Lenalidomide	25 mg	1-21 [£]	22-28	Orally

* Starting dose level

Dialysis includes hemodialysis or peritoneal dialysis.

† The starting dose for patients in Group C accrued to dose level 1 cohort (completed September 2010) was lenalidomide 15 mg post dialysis three times weekly on Days 1-21. Starting with protocol version 5.0, if a return to dose level 1 is indicated, lenalidomide 5 mg on Days 1-21 should be used according to the package insert.

£ When a lenalidomide treatment day occurs on a dialysis day, lenalidomide must be taken after dialysis.

□ Group A: As of November 03, 2010, dose level 1 is completed. Dose level 2 is open.

△ Group B: As of November 03, 2010, dose level 1 is completed. Dose level 2 is open.

◊ Group C: As of November 03, 2010, dose level 1 is completed. Dose level 2 is open.

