# **7. LENALIDOMIDE PHARMACOKINETIC MEASUREMENTS**

The pharmacokinetic sampling will only apply to selected Mayo Clinic patients who are registered in the Phase II portion of this clinical investigation. 5cc of blood will be drawn on Day 6 of Cycle 1: 0 (pre-dose), 0.5, 1, 1.5, 2, 3, 4, 6, 8, 24 hour at all dose groups and at 48 and 72 hour for patients in Group B with severe renal impairment or in Group C on dialysis.

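### The nominal PK day (Cycle 1 Day 6) is a non-dosing day on the every-other-day Group B regimens, and nothing in the plan requires the series to fall on a dosing day

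*Protocol*

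**What the plan says.** Protocol Section 4.0, footnote 6, sets one PK occasion for every dose group, with blood drawn "at the following time points on Day 6 of Cycle 1: 0 (pre-dose), 0.5, 1, 1.5, 2, 3, 4, 6, 8, 24 hr". Further samples follow "at 48 and 72 hr for patients in Group B with severe renal impairment or in Group C on dialysis". SAP Section 7 repeats this ("5cc of blood will be drawn on Day 6 of Cycle 1") without distinguishing regimens. The header of the same Test Schedule states: "Variations of +/- 3 days of the scheduled visits are permitted".

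In Table 7.212, Group B levels 1 and 2 are given "Every other day, days 1-21"; levels 3 and 4 are daily on Days 1 to 21. All Group A levels (Table 7.211) and all current Group C levels (Table 7.213) are daily on Days 1 to 21.

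PK is sampled only in phase II, at the dose that phase I selects for each group (Section 7.12). At this version that dose was still open for Group B: "Group B: As of November 03, 2010, dose level 1 is completed. Dose level 2 is open". Up to 12 patients are planned, with at least two per group (footnote 6). The secondary objective served is "To determine the pharmacokinetics of lenalidomide administration in myeloma patients with impaired renal function" (Section 2.24). Section 16.38 lists Cmax, tmax, AUC, AUC to infinity, CL/F, Vz/F and half-life, and plans to explore their relation to CrCl.

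**The concern.** A series that begins with a pre-dose sample and continues at half-hourly intervals needs a dose at time 0. On an every-other-day regimen started on Day 1 there is none on Day 6. The nominal sampling day and the regimen therefore conflict, and neither document says how to reconcile them.

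Group B is the severe, non-dialysis group. If its PK patients were sampled on a rest day, the comparison of PK parameters across renal function would lack usable peak and exposure values for the group between moderate impairment and dialysis. Exact sampling times would not rescue this, because a peak that was not sampled cannot be recovered afterwards.

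**Working it through.** The plan gives no figure to reproduce; the check is calendar arithmetic. It assumes a first dose on Day 1, no missed doses, doses at the same clock time each dosing day, and a sample due at a dose time drawn just before that dose.

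**1. Dosing days.** Every other day from Day 1 to Day 21 gives Days 1, 3, 5, 7, 9, 11, 13, 15, 17, 19 and 21 (11 doses). Day 6 is not among them. It would be a dosing day only with a start on an even day (2, 4, 6, ...), and no passage states such a start.

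**2. Time since the last dose.** For a series starting on day D, a sample with nominal time t is drawn at 24 × D + t hours on the study clock. Subtracting 24 × (last dosing day) gives the time since dose. For D = 6, t = 8: 24 × 6 + 8 − 24 × 5 = 32 h.

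| Nominal time | Series on Day 6 | Series on Day 5 | Series on Day 7 |
|---|---|---|---|
| 0 | 24 h after Day 5 dose | 48 h after Day 3 dose | 48 h after Day 5 dose |
| 0.5 to 8 h | 24.5 to 32 h after Day 5 dose | 0.5 to 8 h after Day 5 dose | 0.5 to 8 h after Day 7 dose |
| 24 h | 48 h after Day 5 dose, when the Day 7 dose is due | 24 h after Day 5 dose | 24 h after Day 7 dose |
| 48 h | 24 h after Day 7 dose | 48 h after Day 5 dose, when the Day 7 dose is due | 48 h after Day 7 dose, when the Day 9 dose is due |
| 72 h | 48 h after Day 7 dose | 24 h after Day 7 dose | 24 h after Day 9 dose |

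**3. Comparison with the peak.** Protocol Section 1.3 gives time to maximum level as 0.7 to 2.0 h, and Section 1.7 reports no correlation of Cmax or tmax with CrCl. On a Day 6 series the shortest time since dose is 24 h, so no sample lies near the peak or in the first half of the 48 h dosing interval. Cmax, tmax and dosing-interval AUC are not observed, and CL/F, which needs AUC, goes with them. Half-life is not necessarily lost, since a late slope might be estimated from actual times. On a Day 5 or Day 7 series the whole 0 to 24 h profile is captured.

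**4. The visit window.** Day 6 plus or minus 3 is Day 3 to Day 9. It contains four dosing days (3, 5, 7, 9) and three rest days (4, 6, 8), and the nominal target is a rest day. It also admits Day 3, whereas Section 1.4 puts steady state at Day 4.

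**5. Patients affected.** Group B supplies at least 2 PK patients and at most 12 − 2 − 2 = 8.

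**The case against.** The strongest reply is the visit window. PK is a row in the Test Schedule, Day 6 is a column, and footnote 6 sets no narrower window, whereas footnote 16 does so for the 30-day safety visit. A site may therefore sample on Day 5 or Day 7 within the Protocol, and the pre-dose label hints that it should. This stands. A reader might infer that sampling is fixed on Day 6, that Group B patients cannot yield Cmax, tmax or AUC under the plan, or that a site must choose between sampling without a dose and giving an off-schedule dose. The documents do not support any of these, because the window supplies another option. But the window takes no account of regimen and only permits a dosing day; it does not ask for one. SAP Section 7 does not repeat it.

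Second, the problem is conditional. Level 2 being open in phase I does not show that Group B would stop there, and levels 3 and 4 are daily. This stands too.

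Third, a reader might infer that parameters will be computed from wrong nominal times. Nothing says so. Section 14.2 requires drawing times to be recorded, and the SAP leaves PK analysis to a separate report (SAP Sections 2.1 and 8). On the other hand, the sample label in Section 14.27 carries only the date of drug administration, and the diary in Appendix IX asks for the amount taken, not the time. The eCRF is not available, so the dose time may be captured there.

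Finally, PK is a secondary, descriptive objective. It affects neither the MTD nor the response decision in 63 patients.

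**Conclusion.** The concern holds as a missing instruction. The nominal PK day conflicts with the every-other-day Group B regimens, and no passage requires the series to be drawn on a dosing day. If Group B's phase II dose is level 1 or 2, and sites sample on the nominal day, all 2 to 8 Group B PK patients would have no absorption or peak samples, and Cmax, tmax, dosing-interval AUC and CL/F would not be obtainable for them. The loss shrinks to the extent that sites use the window to choose a dosing day, and is nil if Group B goes forward at level 3 or 4. Groups A and C at their assigned daily levels are unaffected.

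The conclusion rests on a Day 1 start, which the regimen wording implies but does not spell out. It is worth correcting because a stated objective is exposed and the remedy is nearly free.

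**What to change.** In footnote 6 and SAP Section 7, state that the PK series is drawn on a scheduled lenalidomide dosing day: Day 6 of Cycle 1 for daily regimens, and Day 5 or Day 7, inside the existing window, for every-other-day regimens. Require the clock time of the dose to be recorded alongside the drawing times, and state in the PK analysis plan that parameters are computed from actual time since dose.

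The cost is one sentence in each document, one recorded time, and a one-day shift of the PK visit for the patients concerned. No dose is added or moved, and sample and patient numbers do not change.

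This does not settle the late samples. On an every-other-day regimen the 48 h sample must precede the dose due then, and the 72 h sample falls 24 h after it. On daily regimens both the 48 h and 72 h samples follow further doses. How these enter the terminal slope and AUC to infinity needs its own rule.
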